4.0 SAFETY ASSESSMENTS AND TOXICITY MONITORING

The study teams at all participating institutions are responsible for protecting the safety, rights and well-being of study participants. Recording and reporting of adverse events that occur during the course of a study help ensure the continuing safety of study participants.

All participants receiving investigational agents and/or other protocol mandated treatment will be evaluated for safety. The safety parameters include all laboratory tests and hematological abnormalities, physical examination findings, and spontaneous reports of adverse events reported by participants. All toxicities encountered during the study will be evaluated according to the NCI criteria specified in the protocol. Life-threatening toxicities must be reported immediately to the DF/HCC Sponsor via the Coordinating Center.

Additional safety assessments and toxicity monitoring will be outlined in the protocol.

4.1 Guidelines for Reporting Serious Adverse Events

Guidelines for reporting Adverse Events (AEs) and Serious Adverse Events (SAEs) are detailed in protocol section 11.

Participating Institutions must report the AEs to the DF/HCC Sponsor and the Coordinating Center following the DFCI IRB SAE Reporting Requirements.

The Coordinating Center will maintain documentation of all Participating Institution Adverse Event reports and be responsible for communicating to all participating investigators, any observations reportable under the DFCI IRB Reporting Requirements. Participating Investigators will review any distributed AE reports, send a copy to their IRB according to their local IRB's policies and procedures, and file a copy with their regulatory documents.

4.2 Guidelines for Processing IND Safety Reports

FDA regulations require sponsors of clinical studies to notify the FDA and all participating investigators of any adverse experience associated with the use of the investigational agent that is both serious and unexpected. The DF/HCC Sponsor will review all IND Safety Reports and ensure that all IND Safety Reports are distributed to the Participating Institutions. The Participating Institutions will review, and submit to their IRB according to their institutional policies and procedures.

5.0 DATA MANAGEMENT

The DF/HCC QACT develops a set of either paper or electronic case report forms (CRF/eCRFs), for use with the protocol. These forms are designed to collect data for each study. The DF/HCC QACT provides a web based training for eCRF users.

5.1 Data Forms Review

When data forms arrive at the DF/HCC QACT, they are reviewed for completeness, protocol treatment compliance, adverse events (toxicities) and response. Data submissions are monitored for timeliness and completeness of submission. Participating Institutions are notified of their data submission delinquencies in accordance with the following:

5.2 Incomplete or Questionable Data

If study forms are received with missing or questionable data, the submitting institution will receive a written or electronic query from the DF/HCC QACT Data Analyst or study monitor. Responses to all queries should be completed and submitted within 14 calendar days. Responses may be returned on the written query or on an amended paper case report form, or in the case of electronic queries, within the electronic data capture (eDC) system. In the case of a written query for data submitted on a paper case report form, the query must be attached to the specific data being re-submitted in response.

5.3 Missing Forms

If study forms are not submitted on schedule, the Participating Institution will receive a Missing Form Report from the Coordinating Center noting the missing forms. These reports are compiled by the DF/HCC QACT and distributed a minimum of four times a year.

6.0 REQUISITIONING INVESTIGATIONAL DRUG

The ordering of investigational agent is specified in the protocol.

Participating Institutions should order their own agent regardless of the supplier (i.e., a pharmaceutical company.)

If the agent is commercially available, check with the local Director of Pharmacy and/or the Research Pharmacy to ensure that the agent is in stock. If the agent is not stocked, ensure that the agent can be ordered once the protocol is approved by the local IRB.

If the agent is investigational, ensure that the pharmacy will be able to receive and store the agent according to state and federal requirements. The local IRB should be kept informed of who will supply the agent (i.e. a pharmaceutical company) so that any regulatory responsibilities can be met in a timely fashion.

7.0 MONITORING: QUALITY CONTROL

The quality control process for a clinical trial requires verification of protocol compliance and data accuracy. The Coordinating Center, with the aid of the QACT provides quality control oversight for the protocol.

7.1 Ongoing Monitoring of Protocol Compliance

The Participating Institutions will be required to submit participant source documents to the Coordinating Center for monitoring. The Participating Institution may also be subject to on-site monitoring conducted by the Coordinating Center.

The Coordinating Center will implement ongoing monitoring activities to ensure that Participating Institutions are complying with regulatory and protocol requirements, data quality, and participant safety. Monitoring will occur before the clinical phase of the protocol begins, continue during protocol performance and through study completion. Additional monitoring practices may include but are not limited to; source verification, review and analysis of the following: eligibility requirements of all participants, informed consent procedures, adverse events and all associated documentation, study drug administration/treatment, regulatory files, protocol deviations, pharmacy records, response assessments, and data management.

Participating institutions will be required to participate in monthly Coordinating Center initiated teleconferences. “Newsletters” highlighting overall protocol progress and important announcements will be distributed as deemed appropriate by the protocol chair.

Virtual monitoring visits will begin after at least 3 participants have been enrolled or after 1 participant has been enrolled if no additional enrollment has occurred in a 6 month period. Virtual monitoring will continue approximately every 6 months and may occur more frequently if there are significant findings or discrepancies. Virtual monitoring will be performed by the Coordinating Center’s Clinical Research Specialist (CRS). The data will be reviewed for completeness, quality, and adherence to the protocol requirements. Sites will be asked to provide de-identified source documentation via fax, email, or mail as specified by the Clinical Research Specialist for all virtual monitoring visits. A virtual site initiation visit (SIV) will be conducted with each participating site prior to study activation. Participating sites may not begin enrolling until the SIV has occurred.

All data submitted to the DF/HCC QACT will be monitored for timeliness of submission, completeness, and adherence to protocol requirements. The Coordinating Center and if applicable, QACT Data Analysts assigned to the protocol, will perform the ongoing protocol data compliance monitoring.

7.2 Evaluation of Participating Institution Performance

7.2.1 Monitoring Reports

The DF/HCC Sponsor will review all Participating site monitoring reports to ensure protocol compliance and to fulfill sponsor responsibilities. The DF/HCC Sponsor may increase the monitoring activities at Participating Institutions that are unable to comply with the protocol, DF/HCC Sponsor requirements or federal and local regulations. Participating Institutions may also be subject to an audit as determined by the DF/HCC Sponsor.

8.0 AUDITING: QUALITY ASSURANCE

Auditing is a method of Quality Assurance. Its main focus is to measure whether standards and procedures were followed. Auditing is the systematic and independent examination of all trial related activities and documents. Audits determine if evaluated activities were appropriately conducted and whether data was generated, recorded and analyzed, and accurately reported per the protocol, Standard Operating Procedures (SOPs), and the Code of Federal Regulations (CFR).

8.1 DF/HCC Sponsored Trials

One on-site audit will be conducted by QACT assuming at least 3 participants are treated at a participating site. An audit may be triggered if deficiencies are noted related to consent practices, eligibility, missing, incomplete, or questionable data submission, or any other issue the protocol chair deems appropriate for audit. If a participating site is selected for audit, approximately 3-4 participants would be audited at the site over a 2 day period. If violations which impact participant safety or the integrity of the study are found, more participant records may be audited.

8.2 Participating Institution

It is the Participating Institution's responsibility to notify the Coordinating Center of all scheduled audit dates (internal) and re-audit dates (if applicable), which involve this protocol. All institutions will forward a copy of final audit and/or re-audit reports and corrective action plans (if applicable) to the Coordinating Center, within 12 weeks after the audit date.

8.3 DF/HCC Sponsor and Coordinating Center

The DF/HCC Sponsor will review all final audit reports and corrective action plans if applicable. The Coordinating Center, must forward these reports to the DF/HCC QACT per DF/HCC policy for review by the DF/HCC Audit Committee. Based upon the audit assessments the DF/HCC Audit Committee could accept or conditionally accept the audit rating and final report. Conditional approval could require the DF/HCC Sponsor to implement recommendations or require further follow-up. For unacceptable audits, the DF/HCC Audit Committee would forward the final audit report and corrective action plan to the DFCI IRB as applicable.

8.4 Sub-Standard Performance

The DF/HCC Sponsor and DFCI IRB are charged with considering the totality of an institution's performance in considering institutional participation in the protocol.

8.5 Corrective Actions

Participating Institutions that fail to meet the performance goals of accrual, submission of timely accurate data, adherence to protocol requirements, and compliance with state and federal regulations, will be recommended for a six-month probation period. Such institutions must respond with a corrective action plan and must demonstrate during the probation period that deficiencies have been corrected, as evidenced by the improved performance measures. Participating Institutions that fail to demonstrate significant improvement will be considered by the DF/HCC Sponsor for revocation of participation.

APPENDIX I: List of Drugs Known to Predispose to Torsades de Pointes

Substantial evidence supports the conclusion that these drugs, when used as directed in labeling, can prolong the QT interval and can have a risk of Torsades de pointes (TdP) in some patients.

Generic Name	Brand Name	Class/Clinical Use	Comments
Amiodarone	Cordarone®	Anti-arrhythmic / abnormal heart rhythm	Females>Males,TdP risk regarded as low
Amiodarone	Pacerone®	Anti-arrhythmic / abnormal heart rhythm	Females>Males,TdP risk regarded as low
Arsenic trioxide	Trisenox®	Anti-cancer / Leukemia	
Astemizole	Hismanal®	Antihistamine / Allergic rhinitis	No Longer available in U.S.
Azithromycin	Zithromax®	Antibiotic / bacterial infection	
Bepidil	Vascor®	Anti-anginal / heart pain	Females>Males
Chloroquine	Aralen®	Anti-malarial / malaria infection	
Chlorpromazine	Thorazine®	Anti-psychotic/ Anti-emetic / schizophrenia/ nausea	
Cisapride	Propulsid®	GI stimulant / heartburn	No longer available in U.S.
Citalopram	Celexa®	Anti-depressant / depression	
Clarithromycin	Biaxin®	Antibiotic / bacterial infection	
Disopyramide	Norpace®	Anti-arrhythmic / abnormal heart rhythm	Females>Males
Dofetilide	Tikosyn®	Anti-arrhythmic / abnormal heart rhythm	Females > Males
Domperidone	Motilium®	Anti-nausea / nausea	Not available in U.S.
Dronedaron	Multaq®	Anti-arrhythmic / Atrial Fibrillation	
Droperidol	Inapsine®	Sedative;Anti-nausea / anesthesia adjunct, nausea	
Erythromycin	E.E.S.®	Antibiotic;GI stimulant / bacterial infection; increase GI motility	Females>Males
Erythromycin	Erythrocin®	Antibiotic;GI stimulant / bacterial infection; increase GI motility	Females>Males
Escitalopram	CipraleX®	Anti-depressant / Major depression/ Anxiety disorders	Changed from Possible Risk to Risk- 12/2/12
Escitalopram	Lexapro®	Anti-depressant / Major depression/ Anxiety disorders	Changed from Possible Risk to Risk- 12/2/12
Flecainide	Tambocor®	Anti-arrhythmic / abnormal heart rhythm	
Halofantrine	Halfan®	Anti-malarial / malaria infection	Females>Males
Haloperidol	Haldol®	Anti-psychotic / schizophrenia, agitation	TdP risk with I.V. or excess dosage
Ibutilide	Corvert®	Anti-arrhythmic / abnormal heart rhythm	Females>Males
Levomethadyl	Orlaam®	Opiate agonist / pain control, narcotic dependence	Not available in U.S.
Mesoridazine	Serentil®	Anti-psychotic / schizophrenia	Removed from US market in 2004
Methadone	Dolophine®	Opiate agonist / pain control, narcotic dependence	Females>Males
Methadone	Methadose®	Opiate agonist / pain control, narcotic dependence	Females>Males
Moxifloxacin	Avelox®	Antibiotic / bacterial infection	
Ondansetron	Zofran®	Somatostatin analog / nausea and vomiting	
Ondansetron	Anset®	Somatostatin analog / nausea and vomiting	
Ondansetron	Zuplenz®	Somatostatin analog / nausea and vomiting	
Ondansetron	Emetron®	Somatostatin analog / nausea and vomiting	
Ondansetron	Ondavall®	Somatostatin analog / nausea and vomiting	

Generic Name	Brand Name	Class/Clinical Use	Comments
Pentamidine	NebuPent®	Anti-infective / pneumocystis pneumonia	Females>Males
Pentamidine	Pentam®	Anti-infective / pneumocystis pneumonia	Females>Males
Pimozide	Orap®	Anti-psychotic / Tourette's tics	Females>Males
Probucol	Lorelco®	Antilipemic / Hypercholesterolemia	No longer available in U.S.
Procainamide	Pronestyl®	Anti-arrhythmic / abnormal heart rhythm	
Procainamide	Procan®	Anti-arrhythmic / abnormal heart rhythm	
Quinidine	Quinaglute®	Anti-arrhythmic / abnormal heart rhythm	Females>Males
Quinidine	Cardioquin®	Anti-arrhythmic / abnormal heart rhythm	Females>Males
Sevoflurane	Ulane®	Anesthetic, general / anesthesia	Label warning for patients with congenital long QT or patients taking QT prolonging drugs
Sevoflurane	Sojourn®	Anesthetic, general / anesthesia	Label warning for patients with congenital long QT or patients taking QT prolonging drugs
Sotalol	Betapace®	Anti-arrhythmic / abnormal heart rhythm	Females>Males
Sparfloxacin	Zagam®	Antibiotic / bacterial infection	No longer available in U.S.
Terfenadine	Seldane®	Antihistamine / Allergic rhinitis	No longer available in U.S.
Thioridazine	Mellaril®	Anti-psychotic / schizophrenia	
Vandetanib	Caprelsa®	Anti-cancer / Thyroid cancer	

APPENDIX J: 11-477 SPECIMEN REQUISITION (Archival Tissue Blocks/Slides and CTC Samples)

Complete this form and include with the specimen shipment. Label ALL materials with participant initials, DFCI participant study ID, and the date and time the specimen was obtained. Include a pathology report with any archival tissue specimens being submitted.

Ship specimen(s) to: [name]
 Dana-Farber Cancer Institute
 [name]
 [name]

Specimen Information

Participant Initials (FML): _____ DFCI Participant Study ID Number: _____ Date specimen(s) shipped: _____

Time Point Pre-study/Baseline Cycle 1 Day 1 Cycle 2 Day 8/Day 9 Off Treatment (without progression)
 Progression on 1st Regimen (Arm A or B) Progression on 2nd Regimen (Arm C) Off Study

Specimen Type (indicate inclusion in shipment by checking box)	Pathology Number(s) or Serial Coding	Quantity submitted	Date specimen obtained	Time specimen obtained (24 Hour Clock)
 Archival tissue block				X
 10-20 unstained slides				X
 CTC (CellSave) tubes				
 Other, specify:				
 Other, specify:				

Responsible contact: _____

Email: _____

Phone number: _____

Site: _____

Mailing address _____

(if blocks need
to be returned): _____

APPENDIX K: 11-477 SPECIMEN REQUISITION (Biopsy/Research Blood)

Complete this form and include with the specimen shipment. Label ALL materials with participant initials, DFCI participant study ID, collection time point and collection date.

Ship specimen(s) to: [name]
 Dana-Farber Cancer Institute
 [name]
 [name]

Specimen Information

Participant Initials (FML): _____ DFCI Participant Study ID Number: _____ Date specimen(s) shipped: _____

Time Point Pre-study/Baseline Cycle 1 Day 1 Cycle 2 Day 8/Day 9 Off Treatment (without progression)
 Progression on 1st Regimen (Arm A or B) Progression on 2nd Regimen (Arm C) Off Study

Specimen Type (indicate inclusion in shipment by checking box)	Quantity submitted	Date specimen obtained
 Biopsy core(s) frozen in OCT		
 FNA samples		
 Fluid biopsy samples		
 Streck tubes		
 Blood in lavender top (EDTA)		
 Other, specify:		
 Other, specify:		

Responsible Contact: _____

Email: _____

Site: _____

Phone number: _____

APPENDIX L: 11-477 SPECIMEN REQUISITION (PBMC Tubes)

Complete this form and include with the specimen shipment. Label ALL materials with DFCI participant study ID, collection time point and collection date and time.

Ship specimen(s) to: [name]
 Whitehead Institute
 [name]
 [name]

Specimen Information

DFCI Participant Study ID Number: _____ Date specimen(s) shipped: _____

PBMC (PAXgene) Tube Time Point (indicate inclusion in shipment by checking box)	Quantity submitted	Collection Date	Collection Time (24 Hour Clock)
 Pre-treatment/Cycle 1 Day 1			
 Cycle 2 Day 8			
 Cycle 2 Day 9			
 Progression on 1 st Regimen (Arm A or B)			
 Progression on 2 nd Regimen (Arm C)			
 Off Treatment (without progression)			
 Off Study			

Responsible Contact: _____

Email: _____

Site: _____

Phone number: _____

DANA-FARBER CANCER INSTITUTE
Nursing Protocol Education Sheet

Protocol Number:	11-477
Protocol Name:	Randomized phase II study of fulvestrant with or without ganetespib in patients with hormone receptor-positive, metastatic breast cancer
DFCI Site PI:	[name]
DFCI Research Nurse:	[name], RN; [name]; [name]; [name]; [name]; [name]

Page the DFCI research nurse or DFCI site PI if there are any questions/concerns about the protocol.
Please also refer to ONC 15: Oncology Nursing Protocol Education Policy
SPECIAL NURSING CONSIDERATIONS UNIQUE TO THIS PROTOCOL

Study Design	
Ganetespib is an HSP90 inhibitor.
 
Fulvestrant is a pure anti-estrogen which is thought to act by downregulating ER expression.
 
Study Design – Section 1.1; Study Rationale – Section 2.4; A cycle is 28 days – Section 5.0

Dose Calc.	
 Ganetespib is in mg/m², calculated by the weight obtained at each treatment visit per DFCI standard of practice. Fulvestrant is flat dosing.
Study Drug & Administration	
Ganetespib administration guidelines are in Sections 5.2 and 7.1
 
 IV, diluted in D5W, administered over 1 hour using a 0.2µm inline filter – Section 7.1.7 Pre-med with dexamethasone and diphenhydramine is required for Cycle 1 and 2. Participants who have successfully tolerated at least 2 cycles of ganetespib ((on Arms B or C) without a hypersensitivity reaction are not required to take the pre meds and is left to the discretion of the treating provider described in Section 5 – see alert page. Loperamide is recommended – Section 5.2.1 Use of vascular access devices (VADs) w/silicone catheters ONLY or peripheral IV is permitted. Use of VADs with catheters made of any other material is prohibited – Sect. 5.2 Administered on Days 1, 8, and 15 of each cycle (3 weeks on, 1 week off) – Section 5.2 See Section 5.5 for management of hypersensitivity reactions 
Fulvestrant administration guidelines are in Sections 5.2 and 7.2
 
 Administered via intramuscular injection into the buttocks on C1, D1; C1, D15; and Day 1 of each subsequent cycle; Sect. 5.2.2 & 7.2.4. NOTE: In Arm C, will only be administered on Day 1 of each cycle; see Alert Page
Dose Modifications and Toxicity	
Dose Modification for toxicity guidelines are in Section 6
 
 Definition of DLT is outlined in Section 5.3 
Ganetespib: See Section 6.2.1 for Dose Reduction Table and Dose Modification Guidelines Table
 
 Diarrhea is expected in most patients. Please see Section 5.5 for diarrhea management guidelines (NOTE: These guidelines were updated on 10/2/2013). Toxicities must recover to ≤ Grade 1 or baseline to resume treatment after skipped doses Criteria to treat: ≤ Grade 2: ANC ≥ 1000/mm³; Platelets ≥ 50,000/ mm³; Hgb ≥ 8.0g/dL Participants may continue on fulvestrant alone if treatment with ganetespib must be discontinued 
Fulvestrant: There are no dose modifications for fulvestrant - See Section 6.2.2

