	2	See Section 5.5	None; If unacceptable to patient or medically concerning despite maximal supportive measures, then skip until recovery to \leq grade 1 (or baseline), up to 21 days*. Restart at same dose**.
	≥ 3		If grade 3 or greater despite maximal supportive measures, skip until recovery to \leq grade 1 (or baseline), up to 21 days*. And then Reduce 1 dose level.
Nausea/vomiting	1 or 2	Treatment as appropriate.	None
	3 (First or 2 nd occurrence)	Treatment as appropriate.	Skip until recovery to \leq grade 1 (or baseline), up to 21 days*. And then Restart at same dose.
	3 (3 rd or more occurrence)		If grade 3 or higher despite optimal prophylactic measures, then skip until recovery to \leq grade 1 (or baseline), up to 21 days*. And then Reduce 1 dose level.
Fatigue	1	No intervention	None
	2	Treatment as appropriate.	None; If unacceptable to patient or medically concerning then hold until recovery to \leq grade 1 (or baseline), up to 21 days*. Restart at same dose**.
	3	Treatment as appropriate.	Skip until recovery to \leq grade 1 (or baseline), up to 21 days*. And then Reduce 1 dose level.
Other non-Hematologic toxicity	1	No Intervention	None
	2	Treatment as appropriate	None; If unacceptable to patient or medically concerning then skip until recovery to \leq grade 1 (or baseline), up to 21 days*. Restart at same dose**.
	2 prolonged or clinically significant and grade ≥ 3	Treatment as appropriate	Skip until recovery to \leq grade 1 (or baseline), up to 21 days And then Reduce 1 dose level*

CONFIDENTIAL

This document is confidential. Do not disclose or use except as authorized.

Toxicity	Grade	Guideline for management	Ganetespiib dose modification*
Infusion reactions	3	Treatment per institutional guidelines for infusion reactions	Contact Principal Investigator to determine whether patient may be retreated
	4	Stop infusion	Permanently discontinue
Thrombocytopenia	1 or 2	No intervention	None
	3	No intervention	Skip until recovery to \leq grade 1 (or baseline), up to 21 days And then Reduce 1 dose level*
Hemoglobin	1 or 2	Treatment as appropriate	None
	3	Treatment as appropriate	Skip until recovery to \leq grade 1 (or baseline), up to 21 days And then Reduce 1 dose level*
Neutropenia	1 or 2	No intervention	None
	3 (ANC < 1,000/ μ L) lasting > 7 days		Skip until recovery to \leq grade 1 (or baseline), up to 21 days And then Reduce 1 dose level*

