Cardiac toxicity	3 (first occurrence of QTc \geq 501 ms on average of triplicate recordings)		Reduce dose level to 120 mg/m ² after the QTc has decreased to at least < 470 ms.
	3 (repeat occurrence of QTc \geq 501 ms on average of triplicate recordings)		Permanently discontinue
	4 (QTc \geq 501 ms or > 60 ms change from baseline and torsades de pointes or polymorphic ventricular tachycardia or signs/symptoms of serious arrhythmia)		Permanently discontinue

* if no recovery after 21 days, patients should go off study

** if dose has been previously held for grade 2 toxicity and grade 2 symptoms recur, OR if the patient finds the symptoms unacceptable, hold dose until recovery to \leq grade 1 and then reduce dose one level

In the case of grade 4 hematologic or non-hematologic toxicity, ganetespiib should be skipped until recovery to grade 1 or less (or baseline), up to 21 days, and then the dose reduced to 150 mg/m². Subjects unable to tolerate ganetespiib at a dose level of 150 mg/m² or whose ganetespiib related toxicity has not returned to baseline or Grade \leq 1 within 21 days should stop ganetespiib. Patients may continue on fulvestrant alone at this time. Once permanently discontinued, ganetespiib should not be restarted.

In the case of a recurrent grade 3 event after prior dose reduction, ganetespiib should be held until the related toxicity has returned to baseline or Grade \leq 1. Subjects should be

CONFIDENTIAL

This document is confidential. Do not disclose or use except as authorized.

reduced by 1 additional dose level (i.e. 2 dose levels from baseline) upon restarting study drug. Only 2 dose reductions are allowed per protocol.

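### Ganetespib dosing rules conflict in two places: the nursing sheet's ANC limit against the Section 6.2.1 neutropenia row, and the Grade 2 rows against their own footnote when the patient finds a first event unacceptable

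*Combined protocol and SAP*

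**What the plan says.** **Neutropenia.** The Nursing Protocol Education Sheet (bound after Appendix L, box on dose modifications and toxicity) gives "Criteria to treat: ≤ Grade 2: ANC ≥ 1000/mm³; Platelets ≥ 50,000/ mm³; Hgb ≥ 8.0g/dL". It attaches no duration to any of the three limits. It names the protocol as its source: "Dose Modification for toxicity guidelines are in Section 6". In the Section 6.2.1 table, Grade 1 or 2 neutropenia needs no change, and the only other neutropenia row is "3 (ANC < 1,000/ μ L) lasting > 7 days", which leads to skipping until recovery and then a one-level reduction. Text below the table separately covers Grade 4 events ("In the case of grade 4 hematologic or non-hematologic toxicity") and Grade 3 events that recur after a reduction. Neither provision has a duration condition.

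**Grade 2 toxicity.** For Grade 2 diarrhea the table cell reads "None; If unacceptable to patient or medically concerning despite maximal supportive measures, then skip until recovery to" Grade 1 or baseline, after which the dose is unchanged, with a double asterisk. The Grade 2 fatigue and other non-hematologic rows follow the same pattern and carry the same marker. The double-asterisk footnote has two triggers. The first is recurrence of Grade 2 symptoms after an earlier Grade 2 hold. The second is "OR if the patient finds the symptoms unacceptable, hold dose until recovery to" Grade 1, and the action for both is then a one-level reduction.

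**Consequence of a reduction.** Section 6.2.1 lists 200, 175 and 150 mg/m², forbids re-escalation and allows two reductions.

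**The concern.** In both places a reader who follows the text as written can take different actions for the same patient, depending on which line is consulted. For neutropenia the sheet is stricter than the section it cites. For Grade 2 toxicity a row and the footnote attached to it prescribe different restart doses for one and the same trigger.

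At stake are consistent ganetespib exposure and dose-reduction data in Arms B and C, and an unambiguous instruction on infusing during Grade 3 neutropenia. Because a reduction cannot be reversed, one taken by following the footnote rather than the row persists for the rest of ganetespib treatment. The sheet carries one institution's heading, and the front sheet plans 56 of 71 patients at DF/HCC. If other sites do not use the sheet (an assumption), the working ANC rule would also differ by site.

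**Working it through.** The plan states no figure to reproduce here. The check sets the texts side by side, case by case.

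**Neutropenia: nursing sheet against Section 6.2.1**

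Calendar B (Section 9.2) schedules blood counts and ganetespib on Days 1, 8 and 15, so a count is available at each dosing visit. The documents give no numerical cut-off for Grade 4 neutropenia, so the cases are defined by grade.

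| Finding on a dosing day | Nursing sheet | Section 6.2.1 |
|---|---|---|
| Grade 1–2 | dose | no change |
| Grade 3, present 7 days or less, no earlier reduction | withhold | no skip instruction |
| Grade 3, present more than 7 days | withhold | skip, then reduce |
| Grade 3 recurring after a reduction | withhold | hold, then reduce further (text below table) |
| Grade 4 | withhold | skip, then reduce (text below table) |

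The two differ only in the second line. A first low count found on a dosing day falls there unless the episode is already known to have lasted more than 7 days. Once the sheet withholds a dose, it also requires recovery to Grade 1 or baseline before treatment resumes, a sequence that the table has not started. For platelets and hemoglobin the table acts on Grade 3 without a duration condition, so this gap is specific to ANC.

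**Grade 2: rows against footnote**

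| Grade 2 event | Row | Footnote | Conflict? |
|---|---|---|---|
| First, unacceptable to the patient | same dose after recovery | one level lower after recovery | yes |
| First, medically concerning only | same dose after recovery | not triggered | no |
| Recurrent after an earlier Grade 2 hold | same dose after recovery | one level lower | no: the footnote works as an escalation of the row |

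**Size of the second conflict, from the starting dose**

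(200 − 175) / 200 = 25 / 200 = 12.5% lower. One of two allowed reductions is used, 1 / 2 = half the allowance.

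**The case against.** The strongest points on the other side are these.

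- **The table does not authorise an infusion at Grade 3 ANC.** A reader might infer that it permits dosing for any episode of 7 days or less. It does not say so. It has no row for that case, and silence is not permission. This stands, and the point is worded accordingly.
- **Two of three infusions per cycle.** A reader might reason that low counts on Day 8 and Day 15 are exactly 7 days apart, so two doses are in dispute. That holds only if the episode began on Day 8. A count found that day may have started earlier, and Section 9 allows ±3 days on assessments and dosing. The mismatch needs only the first low count.
- **Neutropenia may be uncommon here.** It is absent from the list of adverse events above 10% in Section 6.1.1. Section 7.1.12 reports no marrow suppression other than anemia. The neutropenia described in Section 2.1 occurred with docetaxel, which this trial does not use. So the neutropenia half cannot be called routine.
- **The sheet is an education aid.** It refers staff to Section 6 and tells them to page the research nurse or site investigator with questions. That lowers the risk but leaves a numerical limit on the page that its source does not contain.
- **The footnote qualifies the row.** This disposes of the recurrence trigger. It does not dispose of the other one, because the capitalised OR makes the patient's view a separate trigger, and the row already uses that trigger for the opposite restart dose.
- **A third conflict in the other non-hematologic rows.** One might set medically concerning Grade 2 (same dose) against "2 prolonged or clinically significant and grade" 3 or higher (reduce). The terms are loosely separated, but both rest on the investigator's judgment and they do not prescribe different actions for one stated trigger. No conflict is established.

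**Conclusion.** Two conflicts stand. The first is confined to Grade 3 neutropenia of 7 days or less that is not a recurrence after a reduction: the sheet withholds and the table gives no skip instruction. The second is confined to a first Grade 2 diarrhea, fatigue or other non-hematologic event that the patient finds unacceptable. There the row and its footnote contradict each other, and from the starting dose the difference is 200 against 175 mg/m².

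The number of patients affected cannot be derived. A reader might multiply the 47 Arm B patients by the 72% diarrhea rate in Section 6.1.1, but that rate covers all grades and dose levels. Section 2.1 puts diarrhea at about 40% with prophylactic loperamide. Neither figure gives the share that is Grade 2, nor the share that patients would find unacceptable.

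Nor do the documents support a claim that the primary result is compromised. Section 14.2 analyses PFS in all randomized patients whatever their starting dose or early stopping, and the sample size does not depend on these rules. This is an internal inconsistency in the dosing instructions. It should be corrected, but it is not a flaw in the efficacy design.

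**What to change.** Reconcile the Section 6.2.1 table, its double-asterisk footnote and the Nursing Protocol Education Sheet:

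1. State one ANC criterion for giving or skipping ganetespib, identical in the table and the sheet, and covering Grade 3 neutropenia of 7 days or less explicitly.
2. Make the Grade 2 diarrhea, fatigue and other non-hematologic rows and the footnote state the same action for a first event that the patient finds unacceptable, and keep that case distinct from recurrence after an earlier hold.

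The sponsor decides which rule applies in each case. The change amounts to edits to one table, one footnote and one sheet, with no added visits, tests or patients.
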